## List of Abbreviations

BPD	Bronchopulmonary dysplasia
CPAP	Continuous positive airway pressure
ETT	Endotracheal tube
IVH	Intraventricular haemorrhage
LISA	Less invasive surfactant administration
MIST	Minimally invasive surfactant administration
NDAU	Neonatal Data Analysis Unit
NHS	National Health Service
NNRD	Neonatal Network Research Database
R&D	Research and Development
RDS	Respiratory Distress Syndrome
REC	Research Ethics Committee
ROP	Retinopathy of prematurity
SAE	Serious Adverse Events
SUSAR	Suspected Unexpected Serious Adverse Reaction

## 1. Summary

**Title:** The effect of surfactant dose on outcomes in preterm infants with Respiratory Distress Syndrome

**Chief Investigator:** [name]

**Objective:** To assess whether the dose and method of administration of surfactant given to preterm infants with respiratory distress syndrome (RDS) affects neonatal outcomes.

**Research Design:** Prospective observational study using de-identified data from the Neonatal Network Research Database (NNRD) supplemented by additional information on dose, method of surfactant administration and dosing frequency.

**Participant Numbers:** 1300

### **Inclusion Criteria:**

- Gestational age of  $36^{+6}$  weeks +days or less
- Treated with surfactant
- Record of birth-weight available
- Infants born after the initiation date of the study
- Parental opt-out consent

### **Exclusion Criteria:**

- Gestational age of  $37^{+0}$  weeks +days and above

## 2. Introduction

### a. Background

#### *Respiratory Distress Syndrome*

Respiratory distress syndrome (RDS) is a condition that commences shortly after birth and increases in severity during the first 12 to 24 hours. RDS is due, at least in part, to insufficiency of pulmonary surfactant and is mainly confined to preterm infants. Its incidence decreases with increasing gestational age. The aim of RDS management is to minimise lung damage using the least invasive treatment, avoiding unnecessary intubation and mechanical ventilation, enabling normal lung development, preventing bronchopulmonary dysplasia (BDP) and providing respiratory support.

#### *Management of RDS*

The European Consensus Guidelines for the management of RDS recommend stabilisation of the infant using non-invasive respiratory support such as high flow and continuous positive airway pressure (CPAP). The infant's oxygen requirements are monitored and should the fraction of inspired oxygen (FiO2) required increase above 30% in infants under 26 weeks gestational age or 40% in infants over 26 weeks gestational age, then surfactant administration is recommended. Surfactant is normally administered by endotracheal tube whilst the infant is sedated, but the European Consensus Guidelines recommend the Intubate-SURfactant-Extubate (INSURE) method (where the endotracheal tube is extubated within 1 hour) or by less/minimally invasive surfactant administration using a thin catheter to deliver surfactant whilst the infant is spontaneously breathing.

#### *CPAP failure*

The successful management of infants on CPAP means that intubation, surfactant administration and mechanical ventilation can be avoided and a suggestion of lower risk of BDP has been observed. However, between 21%-68% of infants initially managed on CPAP will require mechanical ventilation, termed 'CPAP failure', and defined as "intubation within the first 48-72 hours of starting CPAP" . Furthermore, infants who fail on CPAP have similar outcomes to those who are mechanically ventilated in terms of rates of BDP, mortality, pneumothorax, periventricular haemorrhage and discharge on oxygen .

#### *Surfactant dose*

The licensed dose of surfactant for preterm infants with RDS is 100 to 200mg/kg. A dose of 200mg/kg reduces FiO2 requirements and the need for redosing as well as indicating possibility of reduced mortality and oxygen requirement at 36 weeks post menstrual age. A pharmacokinetic study has also demonstrated that a dose of 200mg/kg results in a higher half-life of surfactant compared to the 100mg/kg.

*Administration techniques*

The drive towards minimally invasive treatments for premature infants as well as the difficulties associated with intubation for surfactant delivery has led to innovations in surfactant administration. Minimally invasive surfactant administration (MIST) or less invasive surfactant administration (LISA) are techniques that use a thin catheter (Angiocath or nasogastric tube) to deliver surfactant whilst the infant is spontaneously breathing and this method is gaining popularity across Europe. A recent meta-analysis found that the use of LISA/MIST has reduced the composite outcome of death or bronchopulmonary dysplasia (BDP) at 36 weeks, need for mechanical ventilation within 72 hours of birth, or need for mechanical ventilation anytime during the neonatal intensive care stay.

Use of the LISA/MIST techniques of surfactant administration also supports the drive towards non-invasive methods of ventilatory support, as no intubation is required to instil the surfactant, in contrast to the intubate-surfactant-extubate (INSURE) method.

**b. Rationale for study**

The rationale for this study is the clinical relevance of understanding whether surfactant dose affects neonatal outcomes in infants with RDS who are treated in the immediate postnatal period.

In a research environment, the dose of surfactant is rigorously controlled, usually administered at a dose of 100mg/kg or 200mg/kg. In clinical practice, clinicians more frequently follow the 'whole vial dosing' approach, where a full vial is given aiming to get as close as possible to the desired dose. Reasons for whole vial use include reduction of waste and administration of surfactant shortly after birth where an infant's weight is unknown. It is unclear whether whole vial dosing leads to under-dosing or over-dosing and whether either situation affects outcomes.

Information regarding the dose of surfactant delivered, and the method of administration, are not currently routinely recorded in the UK.

## The effect of surfactant dose on outcomes in preterm infants with RDS

The aim of this study is to investigate the following objectives:

### *Primary objective*

- To determine whether the first dose of surfactant (100-130 mg/kg compared to 170-200 mg/kg) has an effect on the requirement for mechanical ventilation within four days of birth

### *Secondary objectives*

- To measure the association between first dose of surfactant and:
  - Respiratory support at day 28 post birth (for babies born  $\leq$  32 weeks)
  - Surfactant re-dosing within the first four days of birth
  - Respiratory support at  $36^{+0}$  weeks gestational age (for babies born  $\leq$  32 weeks)
  - Duration of respiratory support
  - $O_2$  at discharge home
  - Respiratory support at 2 years

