### *Secondary endpoints*

- Number of doses of surfactant
- Respiratory support at day 28 post birth
- Respiratory support at  $36^{+0}$  weeks gestational age
- Duration of respiratory support
- Requirement for  $O_2$  at discharge home
- Respiratory support at 2 years

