### a. Comparative fields

In order to investigate whether surfactant dose affects neonatal outcomes, the following data will be obtained from the NNRDs:

	NNRD field	Purpose of using this field for this study
1	Demographics > Birth weight	Using this field alongside the volume of surfactant used, the dose of surfactant will be calculated.
2	Demographics > Sex of the baby (phenotypic)	Characterisation of cohort
3	Demographics > Gestation weeks and day	Inclusion/exclusion criteria
4	Antenatal > Were steroids given during pregnancy?	Characterisation of cohort
5	Antenatal > Number of antenatal steroid courses given	Characterisation of cohort
6	Labour & delivery > Methods of resuscitation	Characterisation of cohort
7	Labour & delivery > Drugs used during resuscitation	Characterisation of cohort
8	Labour & delivery > Was surfactant given during resuscitation?	Characterisation of cohort
9	Respiratory > Respiration: Surfactant given today	Inclusion/exclusion criteria
10	Discharge details > Discharge time and date (anonymised)	Duration of hospitalisation, age at discharge
11	Discharge details > Date of death and time - anonymised	Calculation of mortality
12	Discharge details > cause of death	Determination of outcomes
13	Discharge details > Discharge oxygen	To investigate whether the dose of surfactants can affect whether infants are discharged on oxygen.
14	Respiratory > Respiratory support device and support mode (daily)	To investigate whether using there is a correlation between surfactant dose and respiratory device
16	Discharge details > Clinical diagnoses at discharge	To correlate the dose of surfactant, and/or method of surfactant administration is related to clinical diagnoses at discharge
17	Retinopathy of prematurity > ROP stage*	To determine whether the dose of surfactant is related to the severity of retinopathy of prematurity
18	Cranial ultrasound scan > IVH**	To determine whether the dose of surfactant is related to the severity of periventricular haemorrhage

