## b. Inclusion/Exclusion Criteria

### Inclusion Criteria:

- Gestational age of  $36^{+6}$  weeks or less
- Treated with surfactant
- Record of birth-weight available
- Infants born after the initiation date of the study
- Parental opt-out consent

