### Exclusion Criteria:

- Gestational age of  $37^{+0}$  weeks and above

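### Re-dosing is counted from birth with no limit on age at first dose, so late-treated infants score as not re-dosed for lack of time, and the matching endpoint has no window

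*Protocol*

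**What the plan says.** **Objective.** Protocol, Secondary objectives, lists "Surfactant re-dosing within the first four days of birth" among the outcomes to be related to the first dose. The Exploratory objectives use the same wording for method of administration. The clock starts at birth.

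**Endpoint.** The Secondary endpoints list has "Number of doses of surfactant" instead: a count, with no period attached.

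**Who is included.** Section 4b (and the Summary) requires a gestation of 36+6 weeks or less, "Treated with surfactant", a recorded birth weight, birth after study start and opt-out consent. The only exclusion is a gestation of 37+0 weeks or more. The mITT population in section 6 adds complete baseline factors and evaluability for the primary endpoint. None of these limits age at first dose or asks for a diagnosis.

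**Intended population.** The Summary objective concerns surfactant "given to preterm infants with respiratory distress syndrome (RDS) affects neonatal outcomes". Section 2b speaks of "infants with RDS who are treated in the immediate postnatal period", and the Background describes RDS as a condition that "commences shortly after birth and increases in severity during the first 12 to 24 hours".

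**Data items.** The NNRD Fields section records the time of the initial administration and, on the rescue form, how many doses were given that day. It lists no clock time for repeat doses.

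**The concern.** An infant cannot be re-dosed before being dosed. If the window opens at birth and closes four days later, each infant's chance to show the outcome depends on when the first dose was given. An infant first treated on day 3 has a fraction of the window. One first treated after day 4 has none of it, yet remains in the denominator as not re-dosed. For that infant the four-day ventilation window of the primary endpoint also lies wholly before the exposure it is meant to reflect.

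Section 2a cites less need for re-dosing as an effect of the higher dose, so this outcome bears directly on the study question. A measured rate that depends on time available as well as on dose is hard to interpret. If time available also differed between the 100-130 and 170-200 mg/kg bands, the comparison itself would be distorted. Because the objective and the listed endpoint define different variables, an analyst could follow either.

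**Working it through.** The protocol states no figure on this point, so there is none to reproduce.

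**1. Time at risk.** Input: a window of four days from birth, read as 96 h. With first dose at age *a* hours, time at risk = max(0, 96 − *a*).

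**2. Effect on the observed rate.** The protocol gives no re-dosing rate, so assume that a true proportion *p* of 30% or 40% is re-dosed within 96 h of the first dose.
- Constant hazard: observed risk = 1 − (1 − *p*)^((96 − *a*)/96).
- Variant with all re-dosing within 48 h of the first dose: observed risk = 1 − (1 − *p*)^(min(48, 96 − *a*)/48).

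| Age at first dose | Time at risk | Constant hazard, *p* = 30% | Constant hazard, *p* = 40% | 48 h variant, *p* = 30% | 48 h variant, *p* = 40% |
|---|---|---|---|---|---|
| 0 h | 96 h | 30.0% | 40.0% | 30.0% | 40.0% |
| 12 h | 84 h | 26.8% | 36.0% | 30.0% | 40.0% |
| 24 h | 72 h | 23.5% | 31.8% | 30.0% | 40.0% |
| 48 h | 48 h | 16.3% | 22.5% | 30.0% | 40.0% |
| 72 h | 24 h | 8.5% | 12.0% | 16.3% | 22.5% |
| 96 h or later | 0 h | 0% | 0% | 0% | 0% |

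The loss is certain from 96 h on. Before that it depends on how soon repeat doses follow the first.

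**3. Effect on the dose comparison.** Assume no true dose effect, *p* = 40%, constant hazard, most infants first dosed at 6 h and late ones at 84 h. Observed risks are 1 − 0.6^(90/96) = 38.1% and 1 − 0.6^(12/96) = 6.2%, a gap of 31.9 points. The spurious difference between bands is the difference in late shares times that gap:
- 5% and 5% late: 0 points
- 5% and 10% late: 0.05 × 31.9 = 1.6 points
- 2% and 10% late: 0.08 × 31.9 ≈ 2.5 points
- 5% and 15% late: 0.10 × 31.9 = 3.2 points

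If the late infants had no time at all, the gap would be 38.1 points and the last scenario would give 0.10 × 38.1 = 3.8 points. Equal late shares always give zero.

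**4. Objective against endpoint.** The objective is whether a further dose was given inside a period. The endpoint is a total count over an unstated period. A third dose, or a second one on day 6, changes the endpoint but not the objective's outcome.

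**The case against.** The best defence is that a shortened window lowers the rate in both bands alike unless age at first dose differs between them, and the protocol gives no sign that it does. Age at first dose is in both the propensity model and the outcome model for the primary comparison (section 6). The methods for secondary endpoints may properly sit in the SAP, which is not shown. RDS is described as worsening over the first 12 to 24 hours, and a first dose at 24 h still leaves 72 h. If repeat doses cluster within 48 h of the first, nothing is lost up to 48 h of age.

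Most of this stands and limits the size of the problem. It does not remove it. Balancing age at first dose equalises time at risk between groups, but infants with none are still counted as not re-dosed. The window, the absence of any limit on age at first dose and the mismatch with the endpoint list are fixed in the protocol itself.

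A fair practical objection is that an hour-level window from the first dose cannot be built: repeat doses are recorded only as daily counts, and the delivery-room form has no count. The remedy must therefore work in calendar days.

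**Conclusion.** The point holds as a definitional fault with a modest, unquantified effect. Followed as written, the plan understates re-dosing in late-treated infants, scores those first dosed after day 4 as not re-dosed whatever happens to them, and puts their primary outcome window before their exposure. Bias in the dose comparison is conditional: about 0 to 3 points in the main scenarios, just under 4 in the most unequal one if late infants have no time at all. Those figures rest on an assumed re-dosing rate, hazard and late shares. The protocol gives no distribution of age at first dose.

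Three stronger readings are tempting but unsupported:
- **That whole-vial use ties early treatment to one dose band.** Section 2b gives waste reduction as well as unknown weight as reasons for whole vials, and calls it unclear whether the practice under-doses or over-doses.
- **That infants without RDS dilute every analysis.** Eligibility lets them in, but nothing shows how many there are, and the NNRD Fields section expressly covers prophylactic use, which a strict RDS criterion at dosing would not fit.
- **That the mITT should be cut to first doses in the first day.** The rationale's reference to the immediate postnatal period states an intent, not a cut-off. Such a limit is a design preference and could remove an unknown number of rescue-treated infants.

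**What to change.** 1. Define re-dosing as any further dose within a fixed number of calendar days from the first dose; the number is for the sponsor and investigators. It can be derived from items already planned. On the day of the first dose, a rescue-form count above one is a re-dose, as is any rescue-form dose if the first was given in the delivery room. On later days any dose counts.
2. Use that one definition in the Secondary objectives, the Exploratory objectives and the Secondary endpoints list. If the total number of doses is also wanted, give it a stated period.
3. Exclude from the primary comparison infants whose first dose falls after the four-day window, state this in the mITT definition, and report them descriptively.
4. As a sensitivity analysis only, repeat the primary comparison without infants who have no recorded RDS diagnosis. Discharge diagnoses are recorded after exposure and could be influenced by it, so they should not define the main population.

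**Cost.** Wording changes and no new data items. The study loses an unknown, probably small, number of late-treated infants from the main comparison. Repeat doses are timed to the day, so some variation remains. For example, the day of the first dose plus three more days covers between 72 h and 96 h, depending on the clock time of that dose, compared with 0 h to 96 h under the present wording.

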### *Exploratory objectives*

- Association between method of surfactant administration and:
  - Mechanical ventilation within four days of birth
  - Respiratory support at day 28 post birth (for babies born  $\leq$  32 weeks)
  - Surfactant re-dosing within the first four days of birth
  - Respiratory support at  $36^{+0}$  weeks gestational age (for babies born  $\leq$  32 weeks)
  - Duration of respiratory support
  - $O_2$  at discharge home
  - Respiratory support at 2 years
  - Incidence of complications such as retinopathy of prematurity, and intraventricular haemorrhage
  - Development at 2 years
  - Bayley III score at 2 years
- Association between dose of surfactant and:
  - Respiratory support at 2 years
  - Incidence of complications such as retinopathy of prematurity and intraventricular haemorrhage
  - Development at 2 years
  - Bayley III score at 2 years
- Association between  $FiO_2$  (at point of decision to administer surfactant) and:
  - Mechanical ventilation within four days of birth
  - Respiratory support at day 28 post birth (for babies born  $\leq$  32 weeks)
  - Respiratory support at  $36^{+0}$  weeks gestational age (for babies born  $\leq$  32 weeks)
  - Duration of respiratory support
  - $O_2$  at discharge home

## The effect of surfactant dose on outcomes in preterm infants with RDS

- Association between method of respiratory support in the first two days of life and:
  - Mechanical ventilation within four days of birth
  - Respiratory support at day 28 post birth (for babies born  $\leq$  32 weeks)
  - Respiratory support at  $36^{+0}$  weeks gestational age (for babies born  $\leq$  32 weeks)
  - Duration of respiratory support
  - $O_2$  at discharge home
- Association between use of analgesia and/or sedation at time of surfactant administration and:
  - Mechanical ventilation within four days of birth
  - Respiratory support at day 28 post birth (for babies born  $\leq$  32 weeks)
  - Respiratory support at  $36^{+0}$  weeks gestational age (for babies born  $\leq$  32 weeks)
  - Duration of respiratory support
  - $O_2$  at discharge home
- Association between dose of analgesia and/or sedation at time of surfactant administration and:
  - Mechanical ventilation within four days of birth
  - Respiratory support at day 28 post birth (for babies born  $\leq$  32 weeks)
  - Respiratory support at  $36^{+0}$  weeks gestational age (for babies born  $\leq$  32 weeks)
  - Duration of respiratory support
  - $O_2$  at discharge home

The endpoints for this study are as follows:

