### *Primary endpoint*

- Mechanical ventilation within four days of birth

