## 4. Study Population

### a. Number of Participants

*Proposed sample size: 1300*

The study is powered based on assumed proportions requiring mechanical ventilation within 72 hours of 60% and 45% in the dosing groups 100-130 mg/kg and 170-200 mg/kg respectively. The required power is 80% with the treatment comparison being undertaken at the two-sided 5% level of significance. At the planning stage the proportions of patients falling into the two dosing groups is not known. The sample size for the propensity score matched analysis is determined by the smaller of the two dosing groups and also the ability to find a match for each infant in that group. The table below provides total sample sizes required based on the assumptions set down according to various splits for the proportions of infants in the two dosing groups. Note also that the assumption has also been made that 10% of infants will receive a dose that falls between the upper limit of the lower dose group and the lower limit of the higher dose group. We will also assume that for 25% of infants in the smaller dosing group a match cannot be found. Sample sizes for 90% power are provided for completeness.

The proposed initial sample size of 1300 covers a range of possible assumptions regarding the split across the dosing groups including 45%/45%, 40%/50% and 35%/55%. An interim evaluation of the proportions of infants who fall into the two dosing groups will be undertaken on the first 400 infants recruited into the study to provide a check of the assumed breakdown and a sample size change considered if these assumptions are not correct.

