### *ROC Analysis*

The amount of surfactant dose received (1st dose only) is potentially a key determinant of whether or not an infant requires mechanical ventilation within 4 days of birth. A ROC analysis will be undertaken to explore the ability of dose received to discriminate between those infants who do and those infants who do not require mechanical ventilation over this time period. The ROC analysis plots sensitivity against 1-specificity with points on the ROC curve (AUC) determined by varying the cut-off for dose received. Providing the AUC is greater than 0.7 an optimal cut-off for discrimination purposes will be chosen using Youden's J statistic. A one-sided p-value assessing whether the AUC is significantly greater than 0.5 will also be calculated.

The FiO2 level at the point of decision to administer surfactant is potentially a key determinant of CPAP failure resulting in the requirement for mechanical ventilation within 72 hours of birth. A ROC analysis will be undertaken to explore the ability of FiO2 level to discriminate between those infants who fail on non-invasive methods of ventilation and those infants who do not require mechanical ventilation over this time period. The ROC analysis plots sensitivity against 1-specificity with points on the ROC curve (AUC) determined by varying the cut-off for dose received. Providing the AUC is greater than 0.7 an optimal cut-off for discrimination purposes will be chosen using Youden's J statistic. A one-sided p-value assessing whether the AUC is significantly greater than 0.5 will also be calculated.

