**The effect of surfactant dose on outcomes in preterm infants with RDS**

NNUEpisodes	Discharge details	Cause of death	Cause of death	DEATH CAUSE ICD CODE (DURING NEONATAL CRITICAL CARE PERIOD)	an 6	ICD-10	Specify the major reasons for death of the baby from the list of International Classification of Diseases (ICD) as corresponding with death certificate.	Used to compare outcomes for babies
NNUEpisodes	Discharge details	Discharge:: Oxygen	Discharge Oxygen	RECEIVING OXYGEN THERAPY ON DISCHARGE INDICATOR	N	Delivered from Daily Data Item N No Y Yes	Item specifies if the baby is receiving and is dependant on oxygen therapy on discharge home.	Used to compare outcomes for babies.
NNUEpisodes	Discharge details	Clinical diagnoses at discharge	DiagnosesAtDischarge	DIAGNOSIS (ICD RECORDED ON DISCHARGE FROM NEONATAL CRITICAL CARE) and/or DIAGNOSIS (SNOMED CT ON DISCHARGE FROM NEONATAL CRITICAL CARE)	an 16/n18	ICD-10 and/or SNOMED CT Can be derived from daily records	Specify all the applicable diagnoses for this baby if not already recorded in the daily diagnoses	Used to monitor infant care, evaluate health status and outcomes
Daily	Respiratory	Respiration: Respiratory support device	Respiratory support	RESPIRATORY SUPPORT MODE (NATIONAL NEONATAL DATA SET)	N1	1 Endotracheal tube2 Tracheostomy3 Nasal cannula4 Nasopharyngeal cannula5 Face mask	Type of respiratory support device any time during the 24 hour period (00.00-23.59)	Used to determine level of care
Daily	Respiratory	Respiration: Surfactant given today	DaySurfactantGiven	SURFACTANT GIVEN INDICATOR (ON NEONATAL CRITICAL CARE DAILY CARE DATE)	an 1	N No Y Yes	Records if baby received any dose of surfactant in this day while in the neonatal unit. Surfactant given at delivery/resuscitation is a data	Used to determine health status of infant

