**The effect of surfactant dose on outcomes in preterm infants with RDS**

							item collected separately	
Daily	Respiratory	Respirator mode: Respiratory support mode	Mode of Respiratory Support	RESPIRATORY SUPPORT MODE (NATIONAL NEONATAL DATA SET)	N1	1 Positive pressure ventilation 2 High Frequency Oscillatory Ventilation (HFOV)3 High frequency jet ventilation (HFJV)4 CPAP5 BiPAP/ SiPAP 6 High flow	Mode of respiratory support via endotracheal tube. Conventional ventilation includes intermittent mandatory ventilation, synchronized intermittent mandatory ventilation, assist/control ventilation, pressure support ventilation, pressure targeted, volume targeted, hybrid.	Used to determine level of care
Daily	Medication	Drug given: Medication given on this day	DailyDrugs	MEDICATING GIVEN DURING NEONATAL CRITICAL CARE DAILY CARE DATE (SOMED CT + DM+D)	N1 8	Dm+d code for any drug	Specify the exact medication the baby has received on this day of care	Used for multiple purposes including National Neonatal Audit Programme, monitor outcomes, and derive items for level of care where necessary.
NNUAd hoc	Retinopathy of prematurity screening	ROP stage - left eye	ROPStageLeft	RETINOPATHY OF PREMATURITY STAGE (LEFT EYE)	an 1	0 No ROP1 Stage 1 ROP2 Stage 2 ROP3 Stage 3 ROP4 Stage 4 ROP5 Stage 5 ROPA Aggressive posterior ROP	The ROP stage for the left eye at the relevant ROP screening.	Used in the National Neonatal Audit Programme
NNUAd hoc	Retinopathy of prematurity screening	ROP stage - right eye	ROPStageRight	RETINOPATHY OF PREMATURITY STAGE (LEFT EYE)	an 1	0 No ROP1 Stage 1 ROP2 Stage 2 ROP3 Stage 3 ROP4 Stage 4 ROP5 Stage 5 ROPA Aggressive posterior ROP	The ROP stage for the left eye at the relevant ROP screening.	Used in the National Neonatal Audit Programme

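### Exploratory objective on respiratory support in the first two days: the exposure window lies inside the window of its first outcome, ventilation within four days, so that association is partly built in

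*Protocol*

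**What the plan says.** Protocol section 2b, Exploratory objectives, names an exposure, "Association between method of respiratory support in the first two days of life and", and lists five outcomes under it: mechanical ventilation within four days, respiratory support at day 28, respiratory support at 36+0 weeks, duration of respiratory support, and oxygen at discharge home. The first is worded exactly as the primary endpoint: "Mechanical ventilation within four days of birth".

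The only in-hospital source listed for respiratory support is row 14 of the table in section 3a (Comparative fields): "Respiratory > Respiratory support device and support mode (daily". In Appendix A the mode field holds invasive and non-invasive support as values of one variable. Its list opens with "1 Positive pressure ventilation 2 High Frequency Oscillatory Ventilation" and goes on through jet ventilation to CPAP, BiPAP/SiPAP and high flow. The device field is described as "Type of respiratory support device any time during the 24 hour period (00.00-23.59", so it shows that a device was used on a calendar day, but not in what order.

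For this objective, the protocol does not limit the exposure to non-invasive methods, to the initial method, or to infants not yet ventilated. Nor does it start the outcome after day 2. Section 6 says only that secondary and exploratory endpoints will be analysed.

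**The concern.** An association between a support method and later ventilation can be interpreted only if the method is fixed before the outcome can occur. Here the outcome clock starts at birth and the exposure is still accruing until the end of day 2. During those two days, one daily record of ventilation can supply both the exposure and the event.

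The result could then show a strong link between early support method and ventilation that says nothing about the methods. Comparisons among CPAP, BiPAP and high flow could also shift according to where early failures are placed. Section 10 plans public release of the results, so such an association could be read as evidence about respiratory support.

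**Working it through.** **No plan figure to reproduce.** The sample size table in section 4a concerns the dose comparison. No stated figure belongs to this objective.

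**Step 1: the windows.** Exposure runs from birth to the end of day 2. The outcomes compare with it as follows.

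| Outcome | Relation to days 1-2 |
|---|---|
| Ventilation within four days | Window starts at birth; contains days 1-2 entirely |
| Duration of respiratory support | Days 1-2 count towards the total; partial overlap |
| Support at day 28 | Later; no overlap |
| Support at 36+0 weeks | Later; no overlap |
| Oxygen at discharge home | Later status; not circular |

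**Step 2: two ways to class the exposure.** The protocol does not state the classes, so both are considered.

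- *Invasive ventilation is a class.* An infant ventilated on day 1 or 2 is in that class and is already an event. Risk in the class is 100% whatever the effect of method.
- *Only non-invasive methods are classes.* An infant on CPAP who is intubated on day 1 or 2 can no longer move to high flow within the window, whereas an infant who does not fail still can. The failure therefore affects the class. An infant ventilated throughout days 1-2 has no class at all.

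Section 2a suggests that early failure is not rare. It cites CPAP failure, defined as intubation within 48-72 hours of starting CPAP, in 21% to 68% of infants. It does not split these failures by day.

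**Step 3: illustration of size when invasive ventilation is a class.** Inputs:

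- p = overall event rate. Section 4a assumes 60% and 45% for the two dosing groups. The midpoint is (60 + 45)/2 = 52.5%. These are 72-hour planning rates, used here as a stand-in for a four-day rate.
- s = share of four-day events that fall on days 1-2. The documents do not give it; 25% to 90% is assumed.
- N = 1300 (section 4a).

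Formulas: infants both exposed and events = N × p × s; remaining infants = N × (1 − ps); their events = N × p(1 − s); their risk = p(1 − s)/(1 − ps).

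Worked case, s = 0.90: ps = 0.525 × 0.90 = 0.4725. The remaining infants' risk is 0.0525/0.5275 = 0.100, and the built-in risk ratio is 1/0.0995 = 10.0.

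| s | Exposed and event | Remaining infants | Their events | Their risk | Built-in risk ratio |
|---|---|---|---|---|---|
| 25% | 171 | 1129 | 512 | 45.3% | 2.2 |
| 50% | 341 | 959 | 341 | 35.6% | 2.8 |
| 75% | 512 | 788 | 171 | 21.6% | 4.6 |
| 90% | 614 | 686 | 68 | 10.0% | 10.0 |

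With p from 45% to 60% and the same range of s, the risk ratio runs from 1.9 (p = 60%, s = 25%) to 13.2 (p = 45%, s = 90%). None of this requires any effect of support method.

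**Step 4: what cannot be calculated.** The distortion among CPAP, BiPAP and high flow depends on the classing rule and on failures by day and method. The documents give neither, so no figure is offered.

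**The case against.** The strongest reply is that the protocol fixes two window labels and nothing more. A data dictionary shows what a field can hold, not which values will form the exposure classes. The analysis plan, which is not at hand, could restrict the exposure to non-invasive methods or set a landmark. The authors can frame a question that way: the FiO2 ROC analysis in section 6 contrasts "those infants who fail on non-invasive methods of ventilation and those infants who do not require mechanical ventilation". The objective is also exploratory, and an analyst would quickly notice a class with 100% risk.

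Part of this stands. The 100% risk, and the infinite odds ratio that a reader might infer from it, are conditional on ventilation being an exposure class; the protocol does not say that it is. The size in the working is illustrative only.

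The core is not answered. Both windows are stated in the protocol, so this is not a detail left open. The non-invasive framing in section 6 belongs to a different analysis. Leaving invasive ventilation out of the classes does not remove the problem while early failures stay in the set, because the failure still affects the class. An analysis plan that began the outcome after day 2 would repair the problem, but by answering a different objective from the one written.

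A reader might also infer that the whole objective is unanswerable. The documents do not support that: three of the five outcomes are not circular.

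**Conclusion.** The point holds, within limits. As written, the association between support method on days 1-2 and ventilation within four days is partly circular. The overlap is full for that one outcome and partial for duration of respiratory support. Support at day 28, support at 36+0 weeks and oxygen at discharge are not circular.

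The size cannot be computed from the documents. The illustrative contrast of 100% against about 45% to 10% rests on three assumptions: invasive ventilation is an exposure class, 25% to 90% of events fall on days 1-2, and the midpoint of the 72-hour planning rates stands in for the four-day rate. A reader might take the resulting gap of 55 to 90 percentage points as an estimate of bias in this study. It is not one, because the early share has no source in the protocol.

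Nor does the point reach the primary dose comparison or the sample size, which do not use this exposure.

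**What to change.** For the four-day ventilation outcome, choose one of two changes:

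1. **Landmark at the end of day 2.** Include infants alive and not ventilated by then, class them by non-invasive method on days 1-2, and take new ventilation on days 3-4 as the outcome. State the landmark in the calendar-day units of the daily fields.
2. **Drop this outcome** for this exposure.

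For duration of respiratory support, count from the end of day 2. The other three outcomes do not need a new outcome window.

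An exposure defined as the first method recorded should be used only if order within the day can be obtained. The listed daily fields do not show whether CPAP or intubation came first on the same day.

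**Cost.** This means rewording one exploratory objective and deriving the landmark set from fields already requested. The set is smaller and answers a narrower question, about infants who reach the end of day 2 alive and unventilated. At a 52.5% event rate with 90% of events on days 1-2, it holds 1300 × 0.5275 ≈ 686 infants and 1300 × 0.0525 ≈ 68 events, before removing early deaths. If only 25% fall on days 1-2, it holds about 1129 infants and 512 events. Clinical management does not change.
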